### 5.3 Removal of patients from therapy or study

#### 5.3.1 Patient withdrawal of consent

Patients may voluntarily withdraw from the study treatment, or the study as such, including procedures, at any time at his/her request for any reason. In instances where patient consent is withdrawn, the Investigator must clarify to which degree the patient consent is withdrawn, i.e. whether the patient still is willing to continue to participate in some study specific procedures, or not. The degree of consent withdrawal should be carefully documented in patient files and in study documents.

#### 5.3.2 Screen failures

Screen failures are defined as patients who consent to participate in the clinical study but are not subsequently included in the analysis population due to failure of the eligibility criteria. A minimal set of information is required to be captured (via the eCRF) for such patients to ensure transparent reporting to meet the standards of reporting clinical trials and to respond to queries from regulatory authorities. Minimal information includes age and gender, screen failure details (including failed eligibility criteria), and any SAEs.

#### 5.3.3 Criteria for treatment discontinuation

Patients should be removed from study treatment for any of the following reasons:

- intolerable toxicity in relation to study treatment and adverse events requiring treatment discontinuation according to this protocol (see [Section 4.2](#)),
- pregnancy,
- confirmed tumor progression according to iRECIST criteria (see [Section 12.1](#)),
- any medical condition which may jeopardize the patient's safety if he/she continues trial treatment,
- major protocol violation (including non-compliance to study schedule by the patient) judged to impact safety of the patient or interpretability of the trial,
- decision by the Investigator, Sponsor, or any regulatory authority, that treatment discontinuation is in the best interest of the patient,
- patient withdrawal of consent to receive further study treatment, and
- planned or early termination of the study (see [Section 4.3](#)).

#### 5.3.4 Lost to follow-up

A patient will be considered lost to follow-up if he/she repeatedly fails to return for scheduled visits and is unable to be contacted by the study site.

The following actions must be taken if a patient fails to return to the clinic for a required study visit:

- The site must attempt to contact the patient and reschedule the missed visit as soon as possible, counsel the patient on the importance of maintaining the assigned visit schedule and ascertain whether, or not, the patient wishes to and/or should continue in the study.

In cases in which the patient is deemed lost to follow-up, the Investigator or designee must make every effort to regain contact with the patient (where possible, 3 telephone calls, and if necessary, a certified letter to the patient's last known mailing address, or local equivalent method). These contact attempts should be documented in the patient's medical records.

### ***5.3.5 Criteria for study participation termination***

Reasons for patient withdrawal from the study may include, but are not limited to:

- patient withdrawal of consent for any further trial procedures (see also [Section 5.3.1](#)),
- patient lost to follow-up,
- major protocol violation (including non-compliance to study schedule by the patient) judged to impact safety of the patient or interpretability of the trial,
- decision by the Investigator, Sponsor, or any regulatory authority, that study participation discontinuation is in the best interest of the patient,
- planned or early termination of the study (see [Section 4.3](#)).

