## 3.2 Study endpoints

### 3.2.1 Primary endpoint

- ***The primary endpoint of the phase 1 part*** includes safety and tolerability of EO2401 in combination with nivolumab by a descriptive medical assessment of the combined profile of incidences of adverse events (AEs), treatment-emergent AEs (TEAEs), serious AEs (SAEs), deaths, reasons for treatment discontinuation/delays, and laboratory abnormalities using the NCI-CTCAE v5.0 grading system [60].
- ***The primary endpoint of the phase 2 part*** is the rate of patients without progression (according to iRECIST criteria [37]) or death due to any cause at 6 months after the first dose of randomized treatment. Six months after the first dose of randomized treatment will be determined for each patient and is dependent on the exact time point of evaluation of the CT investigation scheduled at week 25 (day 169). The primary endpoint is to be determined per investigator/local site assessments of progression. The denominator will be all patients who started the randomized treatment in Cohort 2A\* and will be determined for each randomized treatment group separately. Patients will be followed up for progression or death during the first 6 months after start of randomized treatment regardless of whether they stop treatment and continue on other regimens. Patients who

are completely lost to follow-up will be counted as if they had a PFS event during the first 6 months.

\* Cohort 2A = patients with ACC who had prior systemic therapy for established locally advanced or metastatic disease

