There will be a 2-stage consent procedure for the trial, including a first consent for HLA-typing (or the use of already available information in the patients file; such information even if based on testing before the screening period is acceptable) since a large proportion of the patients will not match the HLA-A2 prerequisite to receive the HLA-A2 specific EO2401 immunization compound. The reason for the initial minimized consent (related to the procedure of HLA-testing, and before testing also establishing based on available information that the patient has ACC or MPP, and an age  $\geq 18$  years) is to spare the necessity of all other testing for possible enrollment in the trial for patients who are not known to be HLA-A2 positive. The second stage of the consent procedure will be related to all other aspects of the trial including procedures.

[figure not shown]
Eligible patients who meet the inclusion criteria and do not meet any of the exclusion criteria and have provided informed consent per above will be enrolled in the study.

The procedures for cohort management and enrollment are outlined in a study specific Charter and also described in [Section 6.8](#).

Patients' data will be collected until the clinical data cut-off (see section 4.3.1); the time will be dependent on when the patient is enrolled in the trial; survival follow-up will be collected until patient's death or sponsor's decision to stop the study( see [Section 4.3](#)); the time of study participation might be shorter in individual patients due to individual patient factors

or general trial conduct decisions (e.g. planned trial termination when reaching a pre-specified follow-up time).

[figure not shown]

[figure not shown]
[figure not shown]
Study treatments will be administered until confirmed tumor progression (iRECIST criteria for confirmed tumor progression are to be used; see [Section 12.1](#)), intolerable toxicity, death, patient or Investigator decision, or planned or early termination of the study (see also [Section 5.3](#)). At the time of stopping study treatment, appropriate other treatment will be advised by the Investigator on an individual patient basis. The patient should continue study follow-up measures for as long as the individual patient consent for follow-up is not withdrawn, the site is open, and the study not terminated per plan, or early.

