### 4.3 End of study

#### 4.3.1 *Planned study completion and study duration*

The primary analysis of the study will be performed when the last patient included in the study will reach 6 months of study treatment; additional data will be generated:

after the last patient under treatment has stopped the study treatment.

- Generally, all patients will be followed until death, or until a stable long-term survival outcome has been determined for the respective sub-cohorts of the study; the needed length of survival follow-up for each of the four sub-cohorts of the study differ, and the exact needed duration of survival follow-up time will be data driven. Decision regarding termination of survival follow-up for a specified sub-cohort will be taken by the Sponsor in consultation with the global coordinating investigator.

For administrative purposes, e.g. data cleaning including query resolution, document collection, etc., it is assumed that study sites will remain open approximately 2-3 months after the clinical cut-off.

Study sites will be closed upon study completion. A study site is considered closed when all required documents and study supplies have been collected and a study site closure visit has been performed, except for the sites without any patients included which could be administratively closed by a close-out letter.

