### ***5.3.6 Follow-up of patients discontinued from study treatment or withdrawn from study***

The primary reason for study treatment discontinuation should be documented in the eCRF. In case of treatment discontinuation, patients will complete follow-up visits according to [Section 7.5](#). The first follow-up visit is to be completed 30 days after completion of last dose of study treatment.

In cases of withdrawal from the study, every effort should be made to obtain adequate information. The primary reason for withdrawal from the study should be documented in the eCRF. If possible, patients will complete a follow-up visit according to [Section 7.5.1](#).

In cases with complete informed consent withdrawal (see also [Section 5.3.1](#)), patients will not be followed for any reason, although date of death will be recorded, where applicable and possible to retrieve.

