### ***5.3.7 Procedures for handling incorrectly enrolled patients***

If a patient is found to have been incorrectly enrolled in the study, the Sponsor must be notified as soon as the error is discovered. The Sponsor will decide on the appropriate action to take regarding study treatment and continuation of the patient in the study.

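### Protocol 5.3.5 allows study withdrawal, not only treatment discontinuation, for a protocol violation or non-compliance, which is inconsistent with the follow-up required in 3.2.1, 4.2 and 4.3.1

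*Protocol*

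**What the plan says.** Protocol 5.3.5 opens with "Reasons for patient withdrawal from the study may include, but are not limited to" and includes "major protocol violation (including non-compliance to study schedule by the patient) judged to impact safety of the patient or interpretability of the trial". The identical item stands in 5.3.3, under "Patients should be removed from study treatment for any of the following reasons".

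Section 5.3.6 then treats the two exits differently. A patient who stops treatment completes the Section 7.5 visits. For a patient withdrawn from the study, the site makes every effort to obtain adequate information, and "If possible, patients will complete a follow-up visit according to" Section 7.5.1, the 30-day safety visit. For wrongly enrolled patients, 5.3.7 says: "The Sponsor will decide on the appropriate action to take regarding study treatment and continuation of the patient in the study".

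Three other places set the follow-up rule:
- 3.2.1, on the phase 2 primary endpoint: "Patients will be followed up for progression or death during the first 6 months after start of randomized treatment regardless of whether they stop treatment".
- 4.2: "The patient should continue study follow-up measures for as long as the individual patient consent for follow-up is not withdrawn", with site closure and study termination as the other limits.
- 4.3.1: "Generally, all patients will be followed until death, or until a stable long-term survival outcome has been determined".

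**The concern.** The violation item serves two purposes that should be kept apart. Stopping treatment after a violation leaves the outcome observable. Leaving the study does not, unless follow-up is separately required, and 5.3.6 does not require CT or survival contacts in that case.

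The trigger is broad. The Appendix 4 examples of violations include an excluded concomitant medication, enrolment of an ineligible patient and repeated minor deviations. The visible text gives no criterion for judging that interpretability of the trial is affected, and the trial is open label. Patients who miss visits or take other medication may be those who are getting worse, so removal can be related to outcome.

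At stake are the 6-month outcome in a small randomized group and the assumption of non-informative censoring behind the Kaplan-Meier and Cox analyses of PFS, DOR and OS. This is not the same as excluding collected data from an analysis, because here the outcome may never be collected.

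**Working it through.** The plan states no figure on this point, so there is none to reproduce. The check is of the text first, then of size under stated assumptions.

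**1. What each exit requires**
- Treatment discontinuation (5.3.3, 5.3.6): all of 7.5, that is the safety visit, CT follow-up until confirmed progression (7.5.2) and survival contacts (7.5.3).
- Study withdrawal (5.3.5, 5.3.6): a general effort to obtain information, plus 7.5.1 if possible. The visible list for 7.5.1 contains no CT.
- Complete withdrawal of consent (5.3.6): date of death recorded where this can be retrieved. No matching sentence covers a patient withdrawn for non-compliance, whose survival capture is therefore less explicit.

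Under 4.2, follow-up stops when consent for it is withdrawn, the site closes or the study ends. A violation is not among these reasons.

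**2. Whether the analysis rules cover such a patient**
- Primary endpoint (Protocol 3.2.1, SAP 4.4.1): only patients completely lost to follow-up are counted as events. Under 5.3.4, a lost patient is one the site cannot contact. A patient withdrawn for a violation may well be reachable.
- SAP 7.8.2, visible text: the non-survivor categories are died, alive with progression, and lost to follow-up. None fits a patient withdrawn alive without documented progression. Parts of this section are blacked out and may say more.
- SAP 7.8.5 and 7.8.6: PFS is censored at the last post-baseline CT, DOR follows the same rule, and OS is censored at the last visit.

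**3. Primary 6-month rate**

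Input: 13 treated patients in Cohort 2A-I (SAP 4.2). One patient is 1/13 = 7.7 percentage points. Suppose three patients are known to be progression-free and one other was withdrawn with unknown outcome:
- kept in the denominator, not counted as progression-free: 3/13 = 23.1%
- counted as progression-free: 4/13 = 30.8%
- dropped: 3/12 = 25.0%, which would depart from the stated denominator of all patients who started randomized treatment.

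If that patient was in truth progression-free, the first count is too low. If not, the second is too high.

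**4. Secondary Kaplan-Meier PFS, assumed event times**

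Assume 13 patients with 6 events at week 9, 3 at week 17 and 1 at week 25 (CT weeks from SAP 7.8.1).
- Full follow-up: 7/13 × 4/7 × 3/4 = 23.1%
- One week-17 progressor withdrawn and censored at the week-9 CT: 7/13 × 4/6 × 3/4 = 26.9%
- Two such patients: 7/13 × 4/5 × 3/4 = 32.3%

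**5. The same mechanism spread over all scans**

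Assume exponential times, a scan every 8 weeks, and a fraction w of patients censored at the scan before their progression. If q is the true chance of passing one 8-week interval, the Kaplan-Meier factor per interval becomes q / [1 − w(1 − q)]. The null and target rates are not visible, so true 25-week rates of 20% and 40% are assumed.
- 20%: q = 0.20^(8/25) = 0.5975. Over three intervals the true value is 0.5975³ = 21.3%. With w = 10%: (0.5975/0.9598)³ = 24.1%. With w = 20%: (0.5975/0.9195)³ = 27.4%.
- 40%: q = 0.40^(8/25) = 0.7459, true value 41.5%. With w = 10%: 44.8%. With w = 20%: 48.5%.

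**The case against.** The strongest reply is that this is a tension in permissive wording and not a flat contradiction.
- 5.3.5 says what reasons may include, and 5.3.6 asks for every effort to obtain information. This stands: withdrawal is allowed and not ordered, and some outcomes could still be captured.
- 4.2 itself foresees shorter participation because of individual patient factors or trial conduct decisions, and 3.2.1 speaks of stopping treatment and not of leaving the study. This softens the conflict. It does not say that a violation ends outcome follow-up, and the primary endpoint still needs the 6-month status of every treated patient.
- 9.2 plans survival data for all treated patients or until the sponsor decides, and 4.3.1 generally follows everyone. This supports the fix, because 5.3.6 requires less than these sections intend.
- Some cases are covered. Under SAP 7.8.6, non-trial therapy classified as chemotherapy is a PFS event, and completely lost patients count as events at 6 months. Therapy started after study exit may not be recorded.
- Stage 1 is complete and SAP 7.8.2 now plans only descriptive reporting, so a wording change cannot recover 6-month scans that were not done. This stands and limits the gain.

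A reader might infer that withdrawal inflates the primary 6-month rate by the amounts in step 4. The documents do not support that: the primary endpoint is a simple proportion over all treated patients, and a withdrawn patient counted as not progression-free leaves it unchanged or lowers it. A reader might also infer that 5.3.7 gives the sponsor the same power of removal. It leaves the action open and does not direct an end to follow-up.

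**Conclusion.** The inconsistency is real. A treated patient can be taken out of the study for a violation or non-compliance, after which CT and survival follow-up are not required, although 3.2.1, 4.2 and 4.3.1 call for them.

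The consequence is a possible bias and not a shown one, since no number of such withdrawals is given. For the primary endpoint, one patient is worth 7.7 percentage points of 13, and the direction depends on how that patient is counted. For secondary PFS, DOR and OS, censoring can become informative, with upward bias if the withdrawn patients are deteriorating. Early censoring of one such patient in 13 adds 3.8 points to 6-month Kaplan-Meier PFS (26.9 − 23.1) under the assumed event pattern. The model in step 5 gives 2.8 to 3.3 points at 10% withdrawal. Both illustrations withdraw only patients just before progression, which is the unfavourable case.

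**What to change.** 1. Remove the violation and non-compliance item from 5.3.5. Leave 5.3.3 unchanged, so that no treatment rule is altered.
2. State in 5.3.5, 5.3.6 and 5.3.7 that treated patients taken off treatment for a violation, wrong enrolment or an investigator or sponsor decision continue CT follow-up under 7.5.2 and survival follow-up under 7.5.3, unless consent for follow-up is withdrawn, the patient is lost to follow-up or dies, or the site or study closes.
3. Reword the open-ended introduction of 5.3.5 and its best-interest item to match. Deleting one item alone would leave both as routes to the same removal.
4. For any patient already withdrawn without an event, seek survival status where consent allows. State in SAP 7.8.2 that such a patient stays in the denominator of the 6-month rate as not shown to be progression-free.

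The cost is protocol wording, a note to sites, a sentence in the SAP, and a few CTs and survival contacts that 7.5 already provides for. The main gain is in the remaining CT and survival follow-up.

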### ***5.3.6 Follow-up of patients discontinued from study treatment or withdrawn from study***

The primary reason for study treatment discontinuation should be documented in the eCRF. In case of treatment discontinuation, patients will complete follow-up visits according to [Section 7.5](#). The first follow-up visit is to be completed 30 days after completion of last dose of study treatment.

In cases of withdrawal from the study, every effort should be made to obtain adequate information. The primary reason for withdrawal from the study should be documented in the eCRF. If possible, patients will complete a follow-up visit according to [Section 7.5.1](#).

In cases with complete informed consent withdrawal (see also [Section 5.3.1](#)), patients will not be followed for any reason, although date of death will be recorded, where applicable and possible to retrieve.

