### 3.2.2 Secondary endpoints

The key secondary objectives of the trial are:

- Percentage of patients with shown immunogenicity

[figure not shown]
to EO2316, EO2317, EO2318, and UCP2 that compose EO2401

[figure not shown]
Cross reactivities with the human TAAs IL13Ra2, FOXM1, and BIRC5/survivin will also be evaluated

[figure not shown]
The other secondary endpoints of the trial are:

- ORR, time to response, and DOR as described by RECIST 1.1 [36] and iRECIST criteria [37]; see [Section 12.1](#) for an outline of response criteria.
- PFS as described by RECIST 1.1 and iRECIST criteria, defined as the time interval from the date of first study treatment administration to the date of progression (by RECIST 1.1 or iRECIST criteria) or death due to any cause, whichever is earlier. Patients without progression or death are to be censored at the time of the last tumor assessment.
- OS defined as the time interval from the date of first study treatment administration to the date of death due to any cause. Patients alive will be censored at the date of the last documented follow-up.
- In addition, in the randomized extension of Cohort 2A safety and tolerability of EO2401/nivolumab will be assessed versus internal concurrent controls (groups of patients treated with EO2401 monotherapy and nivolumab monotherapy, respectively), by incidences of adverse events (AEs), treatment-emergent AEs (TEAEs), serious AEs (SAEs); AEs will be analyzed irrespective of relationship, and as related events.

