### 7.5.3 Post-treatment follow-up; Vnnn

Patients will be followed [REDACTED]

At these [REDACTED] timepoints, which if the patient is unable to attend a site visit can be a telephone contact, the following will be done:

- survival status documentation (in case of death, an as precise as possible cause of death is going to be documented),
- documentation of safety; after the post-treatment visit for safety assessment (see [Section 7.5.1](#)) has been made, only SAEs with plausible causal relationship with trial treatment will be documented, and
- if applicable, collection of information regarding further anti-cancer treatments.

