**Table 3 Censoring rules for PFS**

Situation	Date of Event or Censoring
No CT assessment at baseline	Date of first study treatment administration
No progression nor death nor non-trial systemic anti-cancer treatment documented	Date of last post-baseline CT assessment
Death more than [REDACTED] after last post-baseline CT assessment	Date of last post-baseline CT assessment
Death more than [REDACTED] after first study treatment and without post-baseline CT assessment	Date of first study treatment administration
Progression criteria met after $\geq 2$ consecutive schedule missing CT assessments	Date of last post-baseline CT assessment before missing CT assessment
Progression criteria met [REDACTED] after previous CT assessment	Date of previous CT assessment

OS is defined as the period from the first dose of study drug until death due to any cause.

Patients alive at their last visit will be censored at the last visit date.

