### 7.8.7 Analyses of DOR, time-to-OR, PFS and OS endpoints

DOR, DDC, time-to-OR, PFS and OS will be described by KM plots along the number of patients at risk. Separate plots will be created including the curves of following cohorts:

- Cohorts 2A, 2B, 3A, and 3B, non-randomized
- Cohorts 2A, 2B, and 2, non-randomized
- Cohorts 3A, 3B, and 3, non-randomized
- Cohort 2A-I, Cohort 2A-II, and Cohort 2A-III, randomized
- For patients fulfilling and not fulfilling extended in/exclusion criteria of Cohorts 2A, non-randomized

The number of patients with an event of interest and being censored and the median, as well as 1st and 3rd quartiles of the estimated times of interest will be presented with their associated two-sided 95% CIs according to Klein and Moeschberger using a log-log-transformation. If reasonable, non-parametric competing risks techniques will be applied for time-to-OR as a sensitivity analysis, if a non-negligible number of deaths is recorded without earlier objective responses. For PFS and OS, 6-months, 12-months, 18-months, and 24-months PFS/survival estimates and corresponding 95% pointwise confidence limits will be provided in addition.

If the number of events is sufficient, DOR, time-to-OR, PFS and OS will be analyzed using Cox proportional hazards model. For Cohort 2 and 3, non-randomized, the following covariates will be included in the Cox-proportional hazards model

- Primary diagnosis (ACC vs. MPP)
- Previously treated (yes vs. no).

For cohort 2, randomized, the variable cohort (Cohort 2A-I, Cohort 2A-II, vs Cohort 2A-III) will be included in the Cox-proportional hazards model as covariate. No Cox-proportional hazard models will be provided for by patients fulfilling and not fulfilling extended in/exclusion criteria of Cohorts 2A, non-randomized.

All results of the CT scans will be listed.

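### After complete consent withdrawal deaths can still be recorded but being alive cannot, so overall survival censoring depends on outcome and pulls OS estimates downward; the net bias is not always downward

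*Protocol*

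**What the plan says.** Withdrawal can be partial. Protocol 5.3.1 requires that "the Investigator must clarify to which degree the patient consent is withdrawn", and Protocol 4.2 adds that "The patient should continue study follow-up measures for as long as the individual patient consent for follow-up is not withdrawn". A patient who stops treatment but accepts survival contact is still followed: the post-treatment contacts in Protocol 7.5.3 document survival status and may be made by telephone.

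Complete withdrawal is handled separately, in Protocol 5.3.6: "patients will not be followed for any reason, although date of death will be recorded, where applicable and possible to retrieve".

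For the analysis, SAP 7.8.6 states that "OS is defined as the period from the first dose of study drug until death due to any cause". No exclusion of deaths after withdrawal is visible, and SAP 6.1 keeps all data that drop-outs provide. For patients without an event, Protocol 3.2.2 says "Patients alive will be censored at the date of the last documented follow-up" and SAP 7.8.6 says "Patients alive at their last visit will be censored at the last visit date". SAP 7.8.7 plans Kaplan-Meier curves with medians and quartiles, "6-months, 12-months, 18-months, and 24-months PFS/survival estimates and corresponding 95% pointwise confidence limits", and Cox models if there are enough events.

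**The concern.** Take two patients who withdraw completely on the same day. One dies a year later and the death is retrieved: that patient counts as at risk for the whole year and then as an event. The other is alive a year later, but nobody may record it: that patient leaves the risk set at or before withdrawal. The only difference between them is what happened afterwards.

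Kaplan-Meier and Cox methods assume that leaving the risk set says nothing about later outcome. Here it does. Deaths are kept while the matching survivor time is dropped. The effect builds up with time since withdrawal, so the 18- and 24-month estimates are more exposed than the 6-month one. Because retrieval is limited to what is possible, it may also differ between countries and sites.

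**Working it through.** **1. Reading the rules together.** Taken word for word, the SAP sentence would censor anyone alive at the last visit, including patients who die later. That would remove nearly every death, so it cannot be meant. Retrieved deaths must therefore be events, and a complete withdrawer not known to be dead is censored at or before withdrawal.

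**2. Direction, by formula.** The Kaplan-Meier estimate is S(t) = product over death times of (1 − d/n), with d deaths and n at risk. Suppose all deaths are retrieved. Every d is then the same as under full follow-up, but w living withdrawers are missing from the risk set. Since 1 − d/(n − w) ≤ 1 − d/n, the curve cannot lie above the full-follow-up curve. If only some deaths are retrieved, some d are missing too, and the sign depends on who withdraws.

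**3. Size, by simulation.** The plan states no figure to reproduce. Inputs from the documents are median OS of 10.6 months (avelumab trial, Protocol 1.2), 14.8 months (first-line chemotherapy trial, Protocol 1.1.1) and 24.9 months (pembrolizumab trial, Protocol 1.2). The following are assumptions:
- exponential survival, with administrative censoring uniform over 24 to 36 months;
- 5%, 10% or 20% of patients assigned a withdrawal time uniform over the first 12 months (about 3% to 17% withdraw before death or cut-off);
- 100%, 50% or 20% of later deaths retrieved;
- hazard after withdrawal equal to, or twice, that of other patients.

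There were 400,000 simulated patients per scenario. Three rules were compared: (a) full follow-up, (b) the plan's rule, and (c) everyone censored at withdrawal.

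24-month OS with median 24.9 months and 20% assigned to withdraw:

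| Hazard after withdrawal | Deaths retrieved | (a) full | (b) plan | (c) all censored | b − a | c − a |
|---|---|---|---|---|---|---|
| same | 100% | 51.2% | 47.5% | 51.2% | −3.7 | 0.0 |
| same | 50% | 51.3% | 49.4% | 51.4% | −1.9 | +0.1 |
| same | 20% | 51.2% | 50.5% | 51.3% | −0.7 | +0.1 |
| double | 100% | 47.2% | 45.1% | 51.2% | −2.1 | +4.0 |
| double | 50% | 47.2% | 48.0% | 51.2% | +0.8 | +4.0 |
| double | 20% | 47.3% | 50.0% | 51.4% | +2.7 | +4.1 |

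Ranges for b − a at 24 months over all medians and withdrawal fractions:
- same hazard: about 0.5 to 3.7 points lower at 100% retrieval, and 0.2 to 1.9 lower at 50%;
- double hazard: about 0.1 to 2.1 points lower at 100% retrieval, but 0.3 to 1.1 **higher** at 50% and 0.5 to 2.7 **higher** at 20%.

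At 12 months, with the same hazard and full retrieval, the shift is about 0.2 to 1.4 points lower. In that setting a median of 24.9 months falls to about 24.2, 23.6 and 22.4 months at 5%, 10% and 20%.

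Rule (b) lies below rule (c) in essentially every scenario, so the asymmetry itself always pulls down. In the upward cases it is outweighed by the unretrieved deaths of sicker withdrawers.

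**4. Scale.** Of the 70 treated patients, 3% to 17% is 70 × 0.03 ≈ 2 to 70 × 0.17 ≈ 12. Ignoring censoring, the standard error at 50% survival is √(0.5 × 0.5/26) ≈ 9.8 points in non-randomized Cohort 2A and √(0.5 × 0.5/13) ≈ 13.9 points in Cohort 2A-I (sizes from SAP 4.2).

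The Cox models use the same risk sets. How a hazard ratio moves depends on whether withdrawal and retrieval differ between the groups compared; this was not simulated.

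**The case against.** The strongest reply has four parts.

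- **Net direction.** A reader might infer that OS is simply underestimated. The documents do not support that. Protocol 5.3.6 limits recording to deaths that can be retrieved, and nothing is said about the retrieval rate or the prognosis of withdrawers. With sicker withdrawers and partial retrieval the sign reverses. This stands.
- **The obvious repair.** A reader might also infer that censoring every complete withdrawer at withdrawal restores the truth. It does so only if withdrawal is unrelated to prognosis. If hazard doubles after withdrawal, that rule overstates 24-month OS by about 0.7 to 4.1 points, as much as the defect it replaces, and it discards known deaths from an endpoint defined as death from any cause. This stands too.
- **Consequence.** OS is secondary. The phase 2 primary endpoint, the 6-month PFS rate, does not use this rule. SAP 4.3 plans no direct statistical comparison of the randomized groups, and no visible decision rule rests on OS. The shifts are well inside the sampling error of these cohorts. All correct; this limits the priority, but a systematic error is not removed by a wide interval.
- **Stated intent.** Protocol 4.3.1, 9.2 and 10.7 speak of collecting survival for all patients. The specific exception in 5.3.6 most naturally governs complete withdrawers, so these general statements do not close the gap. SAP 5.3 is blacked out, so a provision there cannot be excluded.

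**Conclusion.** The asymmetry is real, and both OS censoring rules allow it. It makes censoring informative for complete withdrawers and pulls OS downward. The net bias is downward when all deaths are retrieved, or when withdrawal is unrelated to prognosis and at least some deaths are retrieved. Otherwise it can be upward.

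Its size cannot be determined from the documents, which give neither a withdrawal rate nor a retrieval rate. Under the assumed 5% to 20% withdrawal it is about 0 to 4 points at 24 months. It would be too strong to call the OS analyses as a whole invalid: the problem is confined to complete withdrawers, who may be few. This is a minor point on a secondary endpoint, worth correcting because the correction is cheap.

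**What to change.** In Protocol 5.3.6 and SAP 7.8.6, where local law and consent allow, establish vital status for **all** complete withdrawers from the same source and at the same check dates: alive or dead, with the date. Count deaths as events and censor the living at the check date. Reword the SAP sentence so that patients not known to have died are censored at the date last known alive, which also brings it into line with Protocol 3.2.2.

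Where such a check is not possible, report the number of complete withdrawers and of deaths retrieved among them. Add a sensitivity analysis that censors all complete withdrawers at withdrawal, and state that it assumes non-informative withdrawal. Do not make that the primary rule.

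The cost is a few sentences in each document and a small amount of extra vital-status checking, limited by local privacy law. The fallback needs no new data.
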